Exploratory Obj 1	ICANS ¹	Medical claim with an ICD-10 code in the IP, non-IP or pharmacy setting for CRS, categorized into the following grades (categorical): Any (all grades and unspecified grade) Grade 1 Grade 2 Grade 3 Grade 4 Grade 5 If patients have multiple, conflicting grades, then the highest recorded grade will be reported	Index date to end of follow-up, where follow-up will be based on last dose of elranatamab (eg, 14 days after last recorded dose or 90 days after last recorded dose). See Section 9.7.6 for censoring criteria
Hematologic events			
Exploratory Obj 1	Anemia ¹	Medical claim with an ICD-10 code in the IP, non-IP, or pharmacy setting for anemia or event in the lab table where hemoglobin is <10g/dL (dichotomous)	Index date to end of follow-up, where follow-up will be based on last dose of elranatamab (eg, 14 days after last recorded dose or 90 days after last recorded dose). See Section 9.7.6 for censoring criteria

Exploratory Obj 1	Neutropenia ¹	Medical claim with an ICD-10 code in the IP, non-IP, or pharmacy setting for lymphopenia or event in the lab table where lymphocyte count is < 1,000 per uL (dichotomous)	Index date to end of follow-up, where follow-up will be based on last dose of elranatamab (eg, 14 days after last recorded dose or 90 days after last recorded dose). See Section 9.7.6 for censoring criteria
Exploratory Obj 1	Lymphopenia ¹	Medical claim with an ICD-10 code in the IP, non-IP, or pharmacy setting for lymphopenia or event in the lab table where lymphocyte count is < 1,000 per uL (dichotomous)	Index date to end of follow-up, where follow-up will be based on last dose of elranatamab (eg, 14 days after last recorded dose or 90 days after last recorded dose). See Section 9.7.6 for censoring criteria
Non-hematologic events			
Exploratory Obj 1	Hypogammaglobulinemia ¹	Medical claim with an ICD-10 code in the IP, non-IP, or pharmacy setting for hypogammaglobulinemia or event in the lab table where IGG value is ≤ 400 mg/dL (dichotomous)	Index date to end of follow-up, where follow-up will be based on last dose of elranatamab (eg, 14 days after last recorded dose or 90 days after last recorded dose). See Section 9.7.6 for censoring criteria

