Exploratory Obj 1	Cytomegaloviral pneumonitis ²	Medical claim with an ICD-10 code in the IP, non-IP, or pharmacy setting for cytomegaloviral pneumonitis (dichotomous)	Index date to end of follow-up, where follow-up will be based on last dose of elranatamab (eg, 14 days after last recorded dose or 90 days after last recorded dose).

			
See Section 9.7.6 for censoring criteria

Exploratory Obj 1	Other pneumonia ²	Medical claim with an ICD-10 code in the IP, non-IP, or pharmacy setting for pneumonia other than adenoviral or cytomegaloviral pneumonia (dichotomous)	
Index date to end of follow-up, where follow-up will be based on last dose of elranatamab (eg, 14 days after last recorded dose or 90 days after last recorded dose).
 
See Section 9.7.6 for censoring criteria

Exploratory Obj 1	Upper respiratory tract infection ²	Medical claim with an ICD-10 code in the IP, non-IP, or pharmacy setting for upper respiratory tract infection (dichotomous)	
Index date to end of follow-up, where follow-up will be based on last dose of elranatamab (eg, 14 days after last recorded dose or 90 days after last recorded dose).
 
See Section 9.7.6 for censoring criteria

Exploratory Obj 1	Sepsis ²	Medical claim with an ICD-10 code in the IP, non-IP, or pharmacy setting for sepsis (dichotomous)	
Index date to end of follow-up, where follow-up will be based on last dose of elranatamab (eg, 14 days after last recorded dose or 90 days after last recorded dose).
 
See Section 9.7.6 for censoring criteria

Exploratory Obj 1 Exploratory Obj 1	Cytomegaloviral infection ²	Medical claim with an ICD-10 code for PJP (dichotomous)	
Index date to end of follow-up, where follow-up will be based on last dose of elranatamab (eg, 14 days after last recorded dose or 90 days after last recorded dose).
 
See Section 9.7.6 for censoring criteria

Exploratory Obj 1	PJP ²	Medical claim with an ICD-10 code for PJP (dichotomous)	Index date to end of follow-up, where follow-up will be based on last dose of elranatamab (eg, 14 days after last recorded dose or 90 days after last recorded dose). See Section 9.7.6 for censoring criteria

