			G62.89, G61.9, G62.9, H46.3, M54.10, M54.18, M79.2, R20.0, R20.1, R20.2, R20.3, R20.8, R20.9	
Any infection	Baseline characteristic - Clinical	Claims data	An ICD-10 Diagnosis Code for any of the following types of infections. See the rows below for codes for each infection type. COVID-19, Adenoviral pneumonia, Cytomegaloviral pneumonitis, Other Pneumonia, Upper respiratory tract infection, Sepsis, Cytomegaloviral infection, PJP, Hepatitis C, Hepatitis B, Other infectious hepatitis, Helicobacter pylori, Candida esophagitis, Urinary tract infection	N/A
Use of intravenous anti-infective	Baseline characteristic - Clinical	Claims data	See “Antivirals,” “Antibiotics,” and “Antifungals” and where service category = injection/infusion drugs or where route = injectable or route array has injectable in it OR HCPCS/CPT codes that indicate IV administration of an anti-infective	N/A
Absolute neutrophil count (for Neutropenia)	Baseline characteristic - Clinical, AE	Claims data	White blood cell count x the percentage of neutrophils White blood cell count: Results_value in the lab results table where the result_abbrev is wbc and result_units are thousand per μ L Percent Neutrophil: Results_value in the lab results table where the result_abbrev is neutrophils percent and result_units are percent White blood cell count and percent neutrophil results must occur on the same day	Severe Chronic Neutropenia International Registry
Neutropenia	Baseline characteristic - Clinical, AE	Claims data	ICD-10 Diagnosis: D70.x or Absolute neutrophil count < 1500 cells per μ L	Kim et al. (2022) Lustberg et al. (2012)

PFIZER CONFIDENTIAL

Redacted

Hypercalcemia	Baseline characteristic - Clinical	Claims data	ICD-10 Diagnosis: E83.52 or value in the GDD table where test is hypercalcemia and result_units are mg/dL and result_value is > 11.5	Kumi et al. (2024) CTCAE v6 (2020)
Hepatotoxicity	Baseline characteristic - Clinical, AE	Claims data	ICD-10 Diagnosis: K71.x	Banerjee et al. (2023)
Amyloidosis	Baseline characteristic - Clinical	Claims data	ICD-10 Diagnosis: E85.4x, E85.8x, E85.9x	Quock et al. (2018)
Hypertension	Baseline characteristic - Clinical	Claims data	ICD-10 Diagnosis: I10x-I15x	Angier et al. (2019)
Extramedullary plasmacytoma	Baseline characteristic - Clinical	Claims data	ICD-10 Diagnosis: C90.2x	Ellington et al. (2021)
CCI score	Baseline characteristic - Clinical	Claims data	See components below	Glasheen et al. (2019)

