Myocardial infarction	Baseline characteristic - Clinical	Claims data	ICD-10 Diagnosis: I21.x, I22.x, I25.2	Glasheen et al. (2019)
Congestive heart failure	Baseline characteristic - Clinical	Claims data	ICD-10 Diagnosis: I11.0, I13.0, I13.2, I25.5, I42.0, I42.5, I42.6, I42.7, I42.8, I42.9, I43.x, I50.x, P29.0	Glasheen et al. (2019)
Peripheral vascular disease	Baseline characteristic - Clinical	Claims data	ICD-10 Diagnosis: I70.x, I71.x, I73.1, I73.8, I73.9, I77.1, I79.0, I79.1, I79.8, K55.1, K55.8, K55.9, Z95.8, Z95.9	Glasheen et al. (2019)

Cerebrovascular disease	Baseline characteristic - Clinical	Claims data	ICD-10 Diagnosis: G45.x, G46.x, H34.0x, H34.1x, H34.2x, I60.x, I61.x, I62.x, I63.x, I64.x, I65.x, I66.x, I67.x, I68.x	Glasheen et al. (2019)
Dementia	Baseline characteristic - Clinical	Claims data	ICD-10 Diagnosis: F01.x, F02.x, F03.x, F04, F05, F06.1, F06.8, G13.2, G13.8, G30.x, G31.0x, G31.1, G31.2, G91.4, G94, R41.81, R54	Glasheen et al. (2019)
Chronic pulmonary disease	Baseline characteristic - Clinical	Claims data	ICD-10 Diagnosis: J40.x, J41.x, J42.x, J43.x, J44.x, J45.x, J46.x, J47.x, J60.x, J61.x, J62.x, J63.x, J64.x, J65.x, J66.x, J67.x, J68.4, J70.1, J70.3	Glasheen et al. (2019)
Rheumatic disease	Baseline characteristic - Clinical	Claims data	ICD-10 Diagnosis: M05.x, M06.x, M31.5, M32.x, M33.x, M34.x, M35.1, M35.3, M36.0	Glasheen et al. (2019)
Peptic ulcer disease	Baseline characteristic - Clinical	Claims data	ICD-10 Diagnosis: K25.x, K26.x, K27.x, K28.x	Glasheen et al. (2019)
Mild liver disease	Baseline characteristic - Clinical	Claims data	ICD-10 Diagnosis: B18.x, K70.0, K70.1, K70.2, K70.3, K70.9, K71.3, K71.4, K71.5, K71.7, K73.x, K74.x, K76.0, K76.2, K76.3, K76.4, K76.8, K76.9, Z94.4	Glasheen et al. (2019)
Moderate or severe liver disease	Baseline characteristic - Clinical	Claims data	ICD-10 Diagnosis: I85.0x, I86.4, K70.4x, K71.1x, K72.1x, K72.9x, K76.5, K76.6, K76.7	Glasheen et al. (2019)
Diabetes without chronic complications	Baseline characteristic - Clinical	Claims data	ICD-10 Diagnosis: E08.0x, E08.1x, E08.6x, E08.8x, E08.9x, E09.0x, E09.1x, E09.6x, E09.8x, E09.9x, E10.0x, E10.1x, E10.6x, E10.8x, E10.9x, E11.0x, E11.1x, E11.6x, E11.8x, E11.9x, E13.0x, E13.1x, E13.6x, E13.8x, E13.9x	Glasheen et al. (2019)

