Cytokine release syndrome (CRS)	AE	Claims data	ICD-10 Diagnosis: D89.83x	Hoover et al. (2024)
Immune effector cell-associated neurotoxicity Syndrome (ICANS)	AE	Claims data	ICD-10 Diagnosis: G92.0x	Hoover et al. (2024)
Anemia	AE	Claims data	ICD-10 Diagnosis: D64.1, D64.2, D64.3, D64.81, D64.89, D64.9 or value in the lab results table where the result_abbrev is hemoglobin and result_units are g per dL and value is <10.0	Kilgore et al. (2021) CTCAE v6.0 (2024)
Lymphocytopenia	AE	Claims data	ICD-10 Diagnosis: D72.810 or value in the lab results table where the result_abbrev is lymphocytes count, result_units are thousand per uL and result_value is <1.5	Papanastasiou et al. (2023) NIH (2022)
Hypogammaglobulinemia	AE	Claims data	ICD-10 Diagnosis: D80.1, D80.3 value in the lab results table where the result_abbrev is IGG, result_units are mg per dL and result_value is ≤ 400	Wallace et al. (2021) Mohan et al. (2024)

PFIZER CONFIDENTIAL

Redacted

Disorders of phosphorus metabolism and phosphatases (including hypophosphatemia)	AE	Claims data	ICD-10 Diagnosis: E83.3	Kim et al. (2023)
Hypokalaemia	AE	Claims data	ICD-10 Diagnosis: E87.6 or value in the lab results table where the result_abbrev is potassium serum and result_units are mmol per L and result_value is < 3.0	Almadani et al. (2024) CTCAE v6.0 (2020)
Arthralgia (joint pain)	AE	Claims data	ICD-10 Diagnosis: M25.5x	Taquet et al. (2022)
Pyrexia (fever)	AE	Claims data	ICD-10 Diagnosis: R50.x	Crabb et al. (2020)
Hypotension	AE	Claims data	ICD-10 Diagnosis: I95.0, I95.81, I95.89, I95.9	Hunley et al. (2021)
Fatigue	AE	Claims data	ICD-10 Diagnosis: R53.x, G93.3x	Cohen et al. (2021)
Nausea or vomiting	AE	Claims data	ICD-10 Diagnosis: R11.x	Peng et al. (2018)
Diarrhea	AE	Claims data	ICD-10 Diagnosis: R19.7, K59.1	Beckman et al. (2015)
Rash	AE	Claims data	ICD-10 Diagnosis: R21	Chen et al. (2022)

PFIZER CONFIDENTIAL

Redacted

Angioedema	AE	Claims data	ICD-10 Diagnosis: D84.1	Sun et al. (2018)
Erythema	AE	Claims data	ICD-10 Diagnosis: L53.0, L53.1, L53.2, L51, L52, L71.0, L71.1, L71.8, L93.0, L93.2, L49.0, L49.1, L49.2, L49.3, L49.4, L49.5, L49.6, L49.7, L49.8, L49.9, L00, L26, L30.4, L53.8, L92.0, L95.1, L98.2, L53.9	Sun et al. (2018)
Muscle spasms	AE	Claims data	ICD-10 Diagnosis: M62.83	Jesus et al. (2022)

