Musculoskeletal pain	AE	Claims data	ICD-10 Diagnosis: M25.50, M25.522, M25.551, M25.552, M25.561, M25.562, M25.572, M25.579, M25.59, M25.612, M25.621, M25.629, M25.631, M25.641, M25.642, M25.652, M25.661, M25.662, M25.669, M25.671, M25.673, M25.674, M25.675, M25.676, M54.6, M54.81, M79.1, M79.12, M79.18, M79.621, M79.622, M79.631, M79.639, M79.641, M79.644, M79.646, M79.652, M79.659, M79.661, M79.662, M79.669, M79.671, M79.673, M79.675, M25.511, M25.512, M25.519, M25.521, M25.529, M25.531, M25.532, M25.539, M25.541, M25.542, M25.549, M25.559, M25.569, M25.571, M25.60, M25.611, M25.619, M25.622, M25.632, M25.639, M25.649, M25.651, M25.659, M25.672, M25.69, M54.89, M54.9, M79.10, M79.11, M79.601, M79.602, M79.603, M79.604, M79.605, M79.606, M79.609, M79.629, M79.632, M79.642, M79.643, M79.645, M79.651, M79.672, M79.674, M79.676	Clinical Classifications Software Refined for ICD-10-CM
COVID-19	AE - infection	Claims data	ICD-10 Diagnosis: U07.1	Pfaff et al. (2023)
Adenoviral pneumonia	AE - infection	Claims data	ICD-10 Diagnosis: J12.0	Cocoros et al. (2024)

Cytomegaloviral pneumonitis	AE - infection	Claims data	ICD-10 Diagnosis: B25.0	ICD-10data.com
Other pneumonia	AE - infection	Claims data	ICD-10 Diagnosis: J12.1, J12.2, J12.81, J12.3, J12.89, J12.9, J13, J18.1, J15.0, J15.1, J14, J15.4, J15.3, J15.20, J15.211, J15.212, J15.29, J15.8, J15.5, J15.6, A48.1, J15.9, J15.7, J16.0, J16.8, A37.01, A37.11, A37.81, A37.91, A22.1, B44.0, J17, B77.81, J18.0, J18.8, J18.9, J10.00, J10.01, J10.08, J11.00, J11.08	Smithee et al. (2020)
Pneumonia	AE - infection	Claims data	An ICD-10 Diagnosis Code for any of the following types of pneumonia. See the following rows for infection type: Adenoviral pneumonia, cytomegaloviral pneumonia, other pneumonia	
Upper respiratory tract infection	AE - infection	Claims data	ICD-10 Diagnosis: A38.0-A38.9, J02.0-J03.91, J01.00-J01.91, J09.x1-J11.89, J00, J04.0-J06.9, H65.00-H65.199, H68.011-H68.019, J20.0-J20.9, J45.20-J45.998, J45.21, J45.31, J45.41, J45.51, J45.901	Butler et al. (2023)
Acute sinusitis	AE - infection	Claims data	ICD-10 Diagnosis: J01.x0	Savage et al. (2023)
Bronchitis	AE - infection	Claims data	ICD-10 Diagnosis: J20.0-J20.9	Butler et al. (2023)
Sepsis	AE - infection	Claims data	ICD-10 Diagnosis: A02.1, A22.7, A26.7, A32.7, A40.0, A40.1, A40.3, A40.8, A40.9, A41.01, A41.02, A41.1, A41.2, A41.3, A41.4, A41.50, A41.51, A41.52, A41.53, A41.59, A41.81, A41.89, A41.9, A42.7, A54.86, B37.7, R65.20, R65.2	Prasad et al. (2021)

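### Table 3 and Annex 2 disagree on the lymphopenia cut-off and the ICANS code, the URTI list takes in chronic J45 claims, and the M-spike unit differs between Table 2 and Annex 2, with no rule on which source prevails

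*Protocol*

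**What the plan says.** Section 9.3 presents Table 3 as the place where outcome variables are defined and sends the reader to Annex 2 for the codes. Section 9.7.6 estimates prevalence and incidence for the adverse events of Table 3. Section 9.8 commits the analysts to following the protocol strictly. None of these says what to do when table and annex differ.

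- **Lymphopenia.** Table 3: "lymphopenia or event in the lab table where lymphocyte count is < 1,000 per uL (dichotomous". Annex 2: "lymphocytes count, result_units are thousand per uL and result_value is <1.5".
- **ICANS.** The Table 3 row reads "Medical claim with an ICD-10 code in the IP, non-IP or pharmacy setting for CRS, categorized into the following grades (categorical", the same wording as the CRS row. Annex 2 gives "ICD-10 Diagnosis: G92.0x" for ICANS and D89.83x for CRS.
- **URTI.** The Annex 2 code list ends with "J20.0-J20.9, J45.20-J45.998, J45.21, J45.31, J45.41, J45.51, J45.901". The chronic pulmonary disease component of the Charlson index in the same annex includes "J40.x, J41.x, J42.x, J43.x, J44.x, J45.x".
- **M-spike (baseline).** Table 2 keeps laboratory records in g/dL; Annex 2 keeps records in mg/dL.
- **Three further rows.** In Table 3, Neutropenia carries the lymphopenia text, Cytomegaloviral infection reads "Medical claim with an ICD-10 code for PJP (dichotomous", and Fatigue lists nausea or vomiting and diarrhea. Annex 2 has separate entries for each: "ICD-10 Diagnosis: D70.x or Absolute neutrophil count < 1500 cells per" uL for neutropenia, B25.x for cytomegaloviral disease, and R53.x with G93.3x for fatigue.

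**The concern.** A programmer told to follow the protocol strictly cannot follow both sources where they conflict. The lymphopenia count would depend on which page was used. ICANS taken from Table 3 would be a second copy of CRS, and the true ICANS frequency would not be reported. The URTI list is a different problem: table and annex agree on the event, but the codes admit claims that the protocol itself treats as chronic lung disease. The M-spike conflict decides which laboratory records enter a baseline table.

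The abstract names CRS, ICANS and infections among the adverse events of interest, and the study is designated a PASS, so readers will look at these rows even though the objective is exploratory.

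**Working it through.** No sample-size or power calculation bears on this. The check sets the sources side by side on one scale.

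**1. Lymphopenia.** Annex 2: 1.5 thousand/uL × 1,000 = 1,500/uL. Table 3: 1,000/uL. The ratio of cut-offs is 1,500 / 1,000 = 1.5. For a patient with no lymphopenia code:

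| Lowest count in window | Table 3 | Annex 2 |
|---|---|---|
| below 1,000/uL | case | case |
| 1,000 to <1,500/uL | not a case | case |
| 1,500/uL or more | not a case | not a case |

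The other laboratory cut-offs given in both places agree: hemoglobin below 10 g/dL, IgG at or below 400 mg/dL, potassium below 3.0 mmol/L. The lymphocyte conflict is isolated.

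**2. ICANS.** The CRS and ICANS rows of Table 3 share the code criterion, the grade list, the follow-up windows and the footnote that sets a 30-day washout. Programmed from Table 3, both the prevalence and the incidence of ICANS would equal those of CRS. Programmed from Annex 2 (G92.0x against D89.83x), they are distinct.

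**3. URTI.** Prevalence in Section 9.7.6 is patients with an event divided by all patients in the cohort, with no exclusion for earlier events. One J45 claim in the window therefore makes a prevalent URTI case. URTI is also part of the baseline variable for any infection, which looks back from the day before index to the MM diagnosis and has no washout. For incident URTI the 60-day washout removes patients with a recent J45 claim, which limits the error there.

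The protocol gives no rate for either condition, so the size is unknown. As an illustration only, let b be the true URTI prevalence and j the share of patients with a J45 claim in the window, and treat them as independent. The reported prevalence is 1 − (1 − b)(1 − j):

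| Assumed b | Assumed j | Reported |
|---|---|---|
| 10% | 3% | 1 − 0.90 × 0.97 = 12.7% |
| 10% | 8% | 1 − 0.90 × 0.92 = 17.2% |
| 20% | 3% | 1 − 0.80 × 0.97 = 22.4% |
| 20% | 8% | 1 − 0.80 × 0.92 = 26.4% |

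**4. M-spike.** 1 g/dL = 1,000 mg/dL. Both sources use the unit to select records and neither states a conversion. A record carries one unit, so the two filters keep sets with no record in common.

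**The case against.** The best defence is that Annex 2 already holds the right codes. Table 3 contains no ICD-10 codes, refers to the annex for them, and the annex is organised by event, so a programmer looking up ICANS would find G92.0x. That is a fair account of what may well happen, and it makes ICANS a wording error with an available correction. It does not settle the lymphocyte cut-off, where both sources state a number. Nor does it settle URTI, where the annex itself is the problem.

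A reader might go further and infer that four adverse events are certainly counted under another event's definition. The documents do not support that. The Neutropenia, Cytomegaloviral infection and Fatigue rows may be faults in how the PDF table was read. Similar shifts appear elsewhere in Table 3: the MM-related cost definitions sit one row out of place, and a vial-size row carries a resource-use count. These three rows need a look at the source document before anything is claimed. The ICANS row is a complete cell with its own grade list, and the lymphocyte, J45 and M-spike conflicts are literal values or codes.

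On J45, the two annex lists serve different purposes and cite different sources, so one code may appear in both. That is true, but it does not explain why a chronic condition should count as an infection event. The contamination is bounded: Table 3 has no composite infection adverse event, and URTI is not in the time-to-infection list.

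On size, the lymphocyte cut-off matters only for patients with laboratory results, and Section 9.7.1 implies that not all have them. Adverse events are exploratory and there is no formal comparison.

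**Conclusion.** The point holds in four parts: an unresolved lymphopenia cut-off (1,000 against 1,500/uL), an ICANS row worded for CRS, a URTI list that counts chronic J45 claims, and a baseline M-spike unit conflict. The first three affect Exploratory Objective 1. M-spike, and J45 through the baseline infection variable, affect Objective 1 descriptives. M-spike is not an adverse event and does not touch the safety tables.

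The effect on reported percentages is unknown. The 1.5 ratio compares thresholds, not lymphopenia rates. The URTI figures rest wholly on assumed inputs and independence. It would also be wrong to predict an ICANS rate of 57.7%: that is the CRS figure from the cited phase 2 trial, and the documents support only that ICANS would match whatever CRS rate this cohort shows, if Table 3 is programmed as written.

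This should be fixed before refresh 4 (20 December 2025) and the final report (28 February 2026).

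**What to change.** 1. Choose one lymphocyte cut-off and state it in both Table 3 and Annex 2.
2. Reword the Table 3 ICANS row to ask for an ICANS code (G92.0x).
3. Remove the J45 entries from the URTI list in Annex 2.
4. State one M-spike unit in Table 2 and Annex 2, matching the unit in the delivered data.
5. Check the Neutropenia, Cytomegaloviral infection and Fatigue rows in the source document. If the text is as it reads here, align them with Annex 2: D70.x or ANC <1500/uL; B25.x; R53.x/G93.3x.
6. Add a sentence saying which source prevails if table and annex differ.
7. Establish which definitions earlier refreshes used, and rerun only the affected tables.

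The cost is text edits, a check of existing code and possibly a rerun of some adverse-event and baseline tables. No new data are needed.

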1	Chronic pulmonary disease	Medical claim with an ICD-10 code in the IP or non-IP setting for chronic pulmonary disease (dichotomous)	180 days prior to index date to index date
1	Rheumatic disease	Medical claim with an ICD-10 code in the IP or non-IP setting for rheumatic disease (dichotomous)	180 days prior to index date to index date
1	Peptic ulcer disease	Medical claim with an ICD-10 code in the IP or non-IP setting for peptic ulcer disease (dichotomous)	180 days prior to index date to index date
1	Liver disease	Medical claim with an ICD-10 code in the IP or non-IP setting for liver disease (dichotomous)	180 days prior to index date to index date
1	Diabetes	Medical claim with an ICD-10 code in the IP or non-IP setting for diabetes (dichotomous)	180 days prior to index date to index date
1	Renal disease	Medical claim with an ICD-10 code in the IP or non-IP setting for renal disease (dichotomous)	180 days prior to index date to index date
1	Hemiplegia or paraplegia	Medical claim with an ICD-10 code in the IP or non-IP setting for hemiplegia or paraplegia (dichotomous)	180 days prior to index date to index date
1	Human immunodeficiency virus	Medical claim with an ICD-10 code in the IP or non-IP setting for human immunodeficiency virus (dichotomous)	180 days prior to index date to index date
1	Metastatic solid tumor	Medical claim with an ICD-10 code in the IP or non-IP setting for metastatic solid tumor (dichotomous)	180 days prior to index date to index date

Objective	Variable	Definition	Assessment Period(s)
1	Albumin serum	Lab event with albumin serum as the test name and g/dL as the result units (dichotomous)	180 days prior to index date to index date
		Most recent numeric value to index date of a lab event with albumin serum as the test name and g/dL as the result units (continuous)	
1	Alanine aminotransferase (ALT)	Lab event with ALT as the test name and IU/L as the result units (dichotomous)	180 days prior to index date to index date
		Most recent numeric value to index date of a lab event with ALT as the test name and IU/L as the result units (continuous)	
1	Aspartate aminotransferase (AST)	Lab event with AST as the test name and IU/L as the result units (dichotomous)	180 days prior to index date to index date
		Most recent numeric value to index date of a lab event with AST as the test name and IU/L as the result units (continuous)	

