Exploratory Obj 1	Hypophosphataemia ¹	Medical claim with an ICD-10 code in the IP, non-IP, or pharmacy setting for hypophosphatemia (dichotomous)	Index date to end of follow-up, where follow-up will be based on last dose of elranatamab (eg, 14 days after last recorded dose or 90 days after last recorded dose). See Section 9.7.6 for censoring criteria

Exploratory Obj 1	Hypokalaemia ¹	Medical claim with an ICD-10 code in the IP, non-IP, or pharmacy setting for hypokalemia or event in the lab table where potassium serum is < 3.0 mmol/L (dichotomous)	Index date to end of follow-up, where follow-up will be based on last dose of elranatamab (eg, 14 days after last recorded dose or 90 days after last recorded dose). See Section 9.7.6 for censoring criteria
Exploratory Obj 1	Hepatotoxicity ¹	Medical claim with an ICD-10 code in the IP, non-IP, or pharmacy setting for hepatotoxicity (dichotomous)	Index date to end of follow-up, where follow-up will be based on last dose of elranatamab (eg, 14 days after last recorded dose or 90 days after last recorded dose). See Section 9.7.5 for censoring criteria
Exploratory Obj 1	Renal failure ²	Medical claim with an ICD-10 code in the IP, non-IP, or pharmacy setting for renal failure (dichotomous)	Index date to end of follow-up, where follow-up will be based on last dose of elranatamab (eg, 14 days after last recorded dose or 90 days after last recorded dose). See Section 9.7.6 for censoring criteria
Exploratory Obj 1	Peripheral neuropathy ¹	Medical claim with an ICD-10 code in the IP, non-IP, or pharmacy setting for peripheral neuropathy (dichotomous)	Index date to end of follow-up, where follow-up will be based on last dose of elranatamab (eg, 14 days after last recorded dose or 90 days after last recorded dose). See Section 9.7.6 for censoring criteria

Exploratory Obj 1	Arthralgia ³	Medical claim with an ICD-10 code in the IP, non-IP, or pharmacy setting for arthralgia (dichotomous)	Index date to end of follow-up, where follow-up will be based on last dose of elranatamab (eg, 14 days after last recorded dose or 90 days after last recorded dose). See Section 9.7.6 for censoring criteria
Hematologic events			

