9.9. Limitations of the Research Methods

While claims databases provide a wealth of comprehensive information to assess patients' demographic and clinical characteristics, a few limitations arise when using such databases. For instance, there may be misclassification of patient records due to provider coding practices (eg, using a diagnosis code as a rule-out criterion) or incorrect coding (eg, data entry errors). As such, the presence of a diagnosis code may not always accurately reflect the presence of disease for an individual patient. Such errors could affect patient eligibility and all variables used to assess treatment characteristics, HCRU, etc. Another potential issue that arises when using any database is generalizability. Oftentimes, the demographic makeup of the dataset is dependent on the providers that supply the information; if a dataset is heavily receiving data from one region of the US, then that might affect overall generalizability.

Databases that contain open and closed claims can offer information in real-time; they often are large in size and have a quick update cadence that allows for the immediate analysis of patient data. However, despite these strengths, there are some limitations associated with the use of open and closed claims. There is a risk of both patient and claim duplication, i.e., where the same patient shows up with a unique patient ID multiple times within the data. With a small cohort size, it may be hard to ascertain if such patients are unique to the dataset or if they are duplicates. Additionally, data providers such as Komodo are beholden to the suppliers of their claims data; therefore, if a data supplier withdraws and no replacement is found, then patient counts could drop across cuts.

Clinical events of interest defined by diagnosis codes may not capture the occurrence or intensity of the disease. Certain conditions, such as hematological toxicities, are often defined via specific cut-offs for certain lab values, which are not often provided in a claims data source. Therefore, ICD codes are used instead. Without lab values, the severity of the disease/grade cannot be determined. Therefore, patients whose AEs were not as severe in grade may not be captured.

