Diabetes with chronic complications	Baseline characteristic - Clinical	Claims data	ICD-10 Diagnosis: E08.2x, E08.3x, E08.4x, E08.5x, E09.2x, E09.3x, E09.4x, E09.5x, E10.2x, E10.3x, E10.4x, E10.5x, E11.2x, E11.3x, E11.4x, E11.5x, E13.2x, E13.3x, E13.4x, E13.5x	Glasheen et al. (2019)

PFIZER CONFIDENTIAL

Redacted

Mild or moderate renal disease	Baseline characteristic - Clinical	Claims data	ICD-10 Diagnosis: I12.9, I13.0, I13.10, N03.x, N05.x, N18.1, N18.2, N18.3, N18.4, N18.9, Z94.0	Glasheen et al. (2019)
Severe renal disease	Baseline characteristic - Clinical	Claims data	ICD-10 Diagnosis: I12.0, I13.11, I13.2, N18.5, N18.6, N19.x, N25.0, Z49.x, Z99.2	Glasheen et al. (2019)
Hemiplegia or paraplegia	Baseline characteristic - Clinical	Claims data	ICD-10 Diagnosis: G04.1, G11.4, G80.0, G80.1, G80.2, G81.x, G82.x, G83.x	Glasheen et al. (2019)
Human immunodeficiency virus	Baseline characteristic - Clinical	Claims data	ICD-10 Diagnosis: B20.x	Glasheen et al. (2019)
Metastatic solid tumor	Baseline characteristic - Clinical	Claims data	ICD-10 Diagnosis: C77.x, C78.x, C79.x, C80.0, C80.2	Glasheen et al. (2019)
Any malignancy	Baseline characteristic - Clinical	Claims data	ICD-10 Diagnosis: C0x.x, C1x.x, C2x.x, C30.x, C31.x, C32.x, C33.x, C34.x, C37.x, C38.x, C39.x, C40.x, C41.x, C43.x, C45.x, C46.x, C47.x, C48.x, C47.x, C48.x, C49.x, C50.x, C51-C58.x, C60-C63.x, C76.x, C80.1, C81.x, C82.x, C83.x, C84.x, C85.x, C88.x, C9x.x	Glasheen et al. (2019)
Albumin serum	Baseline characteristic - Lab	Claims data	An event in the lab results table where the result_abbrev is albumin serum and result_units are g per dL	
ALT	Baseline characteristic - Lab	Claims data	An event in the lab results table where the result_abbrev is ALT and result_units are IU per L	
AST	Baseline characteristic - Lab	Claims data	An event in the lab results table where the result_abbrev is AST and result_units are IU per L	
Neutrophil count	Baseline characteristic - Lab	Claims data	An event in the lab results table where the result_abbrev is neutrophils count and result_units are thousand per μ L	

PFIZER CONFIDENTIAL

Redacted

Creatinine	Baseline characteristic - Lab	Claims data	An event in the lab results table where the result_abbrev is creatinine serum and result_units are mg per dL	
Hemoglobin	Baseline characteristic - Lab	Claims data	An event in the lab results table where the result_abbrev is hemoglobin and result_units are g per dL	

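### Hepatotoxicity is counted from K71.x codes alone although ALT and AST are held in the lab table that defines other adverse events, and rash is coded as an adverse event in Annex 2 but has no row in Table 3

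*Protocol*

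**What the plan says.** **Hepatotoxicity.** Protocol Section 9.3, Table 3, defines the event as "Medical claim with an ICD-10 code in the IP, non-IP, or pharmacy setting for hepatotoxicity (dichotomous". The Annex 2 code list is "ICD-10 Diagnosis: K71.x", with the roles of baseline characteristic and adverse event. The baseline definition in Table 2 is also code-only. The Table 3 row carries the footnote for a 30-day washout.

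**Liver enzymes.** ALT and AST appear in Table 2 as baseline laboratory variables over the 180 days up to index; the ALT row reads "Lab event with ALT as the test name and IU/L as the result units (dichotomous". Annex 2 gives their sources as "An event in the lab results table where the result_abbrev is ALT and result_units are IU per L" and "An event in the lab results table where the result_abbrev is AST and result_units are IU per L", each with a baseline laboratory role only.

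**Other adverse events.** Anemia is a diagnosis code or, in Annex 2, a "value in the lab results table where the result_abbrev is hemoglobin and result_units are g per dL and value is <10.0". Lymphopenia, hypogammaglobulinemia and hypokalaemia are built the same way.

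**Rash.** Annex 2 lists it with the role of adverse event and "ICD-10 Diagnosis: R21". Table 3 goes from diarrhea to angioedema and erythema without a rash row. Section 9.7.6 estimates prevalence and incidence for the Table 3 events and takes washout lengths from that table.

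**Limitations.** Section 9.9 explains the reliance on ICD codes by saying that laboratory cut-offs are often unavailable in claims data, and concludes: "Therefore, patients whose AEs were not as severe in grade may not be captured".

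**The concern.** Exploratory Objective 1 is a table of adverse event percentages that readers will scan row against row. Four rows draw on laboratory evidence after index. Hepatotoxicity does not, although its usual markers are already extracted from the same source. Its percentage therefore depends on whether a clinician entered a K71.x code, while the percentage in the adjacent hypokalaemia row does not depend on coding alone. The protocol gives no reason for the difference, and the general reason in Section 9.9 no longer fits a study that holds laboratory results and uses them for other events.

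Rash raises a different problem. It has a code list but no outcome definition, assessment window or washout, so an analyst who follows the protocol produces no estimate for it.

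**Working it through.** The protocol states no event rate, code sensitivity or laboratory coverage here, so there is no figure to reproduce. The check sets the passages side by side, with one line of set logic.

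**1. Basis of each definition (Table 3 and Annex 2)**
- Anemia: code or hemoglobin, lab results table.
- Lymphopenia: code or lymphocyte count, lab results table.
- Hypogammaglobulinemia: code or IgG, lab results table.
- Hypokalaemia: code or serum potassium, lab results table.
- Hepatotoxicity: code only; ALT and AST are in the lab results table but used only up to index.
- Renal failure: code only in Table 3; creatinine is in the lab results table but used only up to index.

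Neutropenia is left out of this comparison because its Table 3 row repeats the lymphopenia definition.

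Table 3 therefore follows no uniform rule. Hepatotoxicity is one of two events left on codes while a related marker is held.

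**2. Direction**

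Let C be the patients with a K71.x claim in follow-up and L those with a qualifying ALT or AST result. Then |C ∪ L| = |C| + |L \\ C| ≥ |C|. The code-only count equals or falls below the code-or-lab count. This fixes the direction of the difference between two definitions; it does not say which count is nearer the truth.

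**3. Size**

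Suppose codes capture a share s of true liver events, a share f of patients has follow-up results, results identify every event where present and add no false ones, and the two are independent. The ratio of the counts is then

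[1 − (1 − s)(1 − f)] / s = 1 + f(1 − s)/s.

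Neither s nor f is in the documents. With both assumed anywhere from 20% to 80%:
- s = 0.8, f = 0.2: 1 + 0.2 × 0.2/0.8 = 1.05.
- s = 0.2, f = 0.8: 1 + 0.8 × 0.8/0.2 = 4.2.

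A range from almost no difference to a fourfold one reflects only the assumptions. It shows that the gap cannot be sized from the protocol and should not be quoted as an effect.

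**4. Rash**

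Of the conditions with an adverse event role in Annex 2, rash is the only one without a counterpart in Table 3. Section 9.3 presents Table 3 as the full list of outcome variables, and Section 9.7.6 is tied to it. No other section mentions rash.

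**5. Follow-up window**

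The hepatotoxicity row refers to Section 9.7.5 for censoring, while the other adverse event rows refer to Section 9.7.6. Both sections list the same four censoring events, so the pointer needs correcting but does not change the count.

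**The case against.** The code-only definition is internally consistent. Table 2, Table 3 and Annex 2 agree, and Annex 2 cites a source for the code list. It applies to every patient in both cohorts, whereas laboratory results cover only some; Section 9.7.1 plans a comparison of patients with and without a laboratory observation for that reason. Section 9.9 discloses the general weakness of codes, and renal failure is handled the same way. All of this stands. It makes the hepatotoxicity point one of comparability between rows and unused data, not a contradiction.

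Three stronger readings are tempting, and the documents support none of them.
- A reader might infer that every patient with raised transaminases and no K71.x claim is a missed case. A raised ALT or AST is not by itself hepatotoxicity, so a higher count is not automatically a more accurate one.
- A reader might infer that version 2.0 moved the other events to a code-or-lab basis and overlooked the liver. The amendment log ties the laboratory additions to Table 2 and the Annex; its Table 3 entry lists administrations, inpatient visit sources and step-up resource use.
- A reader might infer that rash was meant to be reported and was dropped. It may equally be a leftover code entry: graft versus host disease also sits in Annex 2 without a row in Table 2. Nor can a row lost when the PDF was read be excluded, since the nearby fatigue row carries the nausea/vomiting and diarrhea definitions.

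**Conclusion.** The point holds as a minor one. Hepatotoxicity is reported on a narrower basis than four other laboratory-detectable events in the same table, without a stated reason, although ALT and AST are in hand. The direction of the difference is certain by set logic; its size is unknown, and no assumed percentage should be attached to it. The rash mismatch is the firmer part: on the text available, Annex 2 and Table 3 disagree and the plan as written yields no rash estimate. That conclusion assumes Table 3 has no rash row in the source document. Both parts affect an exploratory, descriptive objective with no formal comparison between cohorts, and neither touches the primary objectives.

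**What to change.** - **Hepatotoxicity.** Keep the K71.x figure for the whole cohort. Add to Table 3 and Annex 2 a supplementary code-or-lab figure with an ALT/AST cut-off, and the units or reference limit it relies on, prespecified and justified by the sponsor. Apply the same 30-day washout and the same 14-day and 90-day follow-up windows. Report it among patients with at least one follow-up ALT or AST result, and state what share of each cohort that is. Point the row's censoring reference to Section 9.7.6. If the sponsor prefers to remain on codes alone, give the reason in the protocol, and do the same for renal failure.
- **Section 9.9.** Revise the explanation for using ICD codes so that it separates the events with a laboratory criterion from those without one.
- **Rash.** Reconcile Annex 2 with Table 3. Either add a rash row with a washout footnote, for example the 14-day one already used for erythema and angioedema, or delete the Annex entry if rash is not intended.

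The cost is a few lines of definition and programming on data already licensed. The downside is two hepatotoxicity figures, one of them in a subset whose size and make-up must be shown.
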